## 5.9 Statistical considerations

### 5.9.1 Statistical design, method and analytical procedures

Case data will be analyzed by an independent third-party biostatistician using a statistical modeling software tool (PASS or MATLAB).

The primary endpoint is the relative detection rate (sensitivity) between mpMRI and micro-ultrasound for significant prostate cancer at a subject level. Power is based on the sensitivity of the test. Prevalence is assumed to be 60%.

H0: Sensitivity of micro-ultrasound/Sensitivity of mpMRI  $\leq \delta = 0.76$

H1: Sensitivity of micro-ultrasound/Sensitivity of mpMRI  $> \delta = 0.76$

where  $\delta$  was based on results of comparing mpMRI to TRUS as noted below.

Specificity will be similarly tested. That is:

H0: Specificity of micro-ultrasound/ Specificity of mpMRI  $\leq \delta = 0.67$

H1: Specificity of micro-ultrasound/ Specificity of mpMRI  $> \delta = 0.67$

These analyses will be conducted at the subject level.

#### Non-inferiority Margin, $\delta$

In the PROMIS study, the most recent confirmatory study of mpMRI to TRUS, mpMRI showed improvement in sensitivity of MP-MRI to TRUS from 0.93 to 0.48, respectively, with a test ratio of 0.52 (95% CI: 0.45-0.60) using McNemar's test. In order to preserve the effect of mpMRI versus TRUS as seen in this study, the non-inferiority margin for the test ratio of 0.76 (24%) was chosen as being equal to 50% of the effect from the point estimate of 0.52 to a ratio of unity (equal sensitivity). Then, the lower bound of the test ratio must not exceed 0.76 in order for non-inferiority to be declared in the current trial, thus preserving at least 50% of the effect of mpMRI versus TRUS. McNemar's test will be used to establish the (1- $\alpha$ ) confidence interval for the test ratio.

Specificity from the same study was lower on mpMRI than TRUS with a test ratio of 2.34 (2.08–2.68). In the prostate biopsy procedure, since sampling is required regardless of imaging outcome (systematic sampling), specificity is less important. Still, we would like to preserve a reasonable specificity similar to mpMRI, therefore we select a non-inferiority margin of 0.67, or not more than 50% worse than the existing difference between mpMRI and TRUS (2.34\*1.5 ratio to TRUS, 1/1.5=0.67 ratio to mpMRI).

Details of the design are presented in section 5.8.1.

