### **5.9.3 Level of significance and power of the clinical investigation**

Assuming a micro ultrasound sensitivity of 0.85 and mpMRI performs at an expected 0.90 sensitivity, then 120 subjects would be required to provide 80% power to reject the null hypothesis, assuming 80% agreement between the methods.

PASS and MATLAB software were used for sample size calculations.

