Sensitivity of mpMRI has varied widely in the literature as demonstrated by numerous meta-analyses, showing detection rates ranging from 24%-87%. The PROMIS trial found a sensitivity of 88% for predicting clinically significant prostate cancer, but did not perform targeted biopsy. Therefore, this value could be seen as a maximum possible when perfect targeting and histopathology is assumed. In cases with targeted biopsy, such as the PRECISION trial, mpMRI detected significant cancer in 38% of the arm vs. 26% in the systematic biopsy arm. Assuming a similar 54% incidence this amounts to sensitivities of 70% and 48% respectively which compare well with our own feasibility cohorts demonstrating sensitivities of 56-85% for mpMRI and previously discussed sensitivity data for systematic biopsy.

Sensitivity data on micro-US is available from 2 cohort studies and 1 randomized trial. These three datasets suggest sensitivities of 83% (N=60), 98% (N=79), and 61% (N=286) for a weighted average of 71%. While this average is biased towards the earlier data from the randomized trial, this study was conducted on an early version of the device with little training on the PRI-MUS risk identification protocol, therefore we expect this to underestimate the true sensitivity of the micro-US modality.

Given an incidence of approximately 50% with sensitivities of mpMRI and Micro-US of approximately 66% and 75% respectively, 108 subjects are required to provide 80% confidence of achieving non-inferiority within 20%. This non-inferiority bound was chosen to maintain at least 50% of the benefit of mpMRI over conventional systematic biopsy providing a sensitivity of approximately 48%.

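### Meeting the 0.76 margin does not secure 'at least 50%' of the mpMRI-over-TRUS effect: it retains 50% at the historical point estimate, 40% at that estimate's upper confidence limit, and less at lower mpMRI sensitivities

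*Combined protocol and SAP*

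**What the plan says.** Section 5.9.1 tests the ratio of micro-ultrasound to mpMRI sensitivity against 0.76, and section 5.9.5 applies the test through a one-sided 95% lower confidence bound. The margin text takes sensitivities of 0.93 (mpMRI) and 0.48 (TRUS) from one historical paired study, "with a test ratio of 0.52 (95% CI: 0.45-0.60) using McNemar's test". It then says that "the non-inferiority margin for the test ratio of 0.76 (24%) was chosen as being equal to 50% of the effect from the point estimate" to a ratio of 1, and describes the result as "thus preserving at least 50% of the effect of mpMRI versus TRUS".

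Other parts of the document give other mpMRI sensitivities:

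- Section 5.9.3 assumes 0.90 for power.
- Section 5.20 says that the same historical study "found a sensitivity of 88% for predicting clinically significant prostate cancer". Because that study did not use targeted biopsy, it adds that "this value could be seen as a maximum possible when perfect targeting and histopathology is assumed".
- For mpMRI with targeted biopsy against systematic biopsy, section 5.20 derives "sensitivities of 70% and 48% respectively". It then uses about 66% for mpMRI in an enrolment calculation.
- Section 5.20 also chooses the 48% for TRUS systematic biopsy to define the non-inferiority threshold.

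**The concern.** The phrase 'at least 50%' is an unconditional statement about what a pass would show. A margin halfway from a point estimate to 1 has that property only if the estimate is correct or overstates the TRUS/mpMRI ratio. The plan prints the confidence interval but does not use it. The mpMRI figure behind the estimate is the highest one in the document, and it is an image-reading sensitivity, whereas this trial measures detection by biopsy. If mpMRI performs less well here, the gap between mpMRI and systematic biopsy narrows and a fixed ratio of 0.76 gives away more of it.

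At stake is the sentence that could be written after a pass. A lower bound just above 0.76 could be reported as showing that micro-ultrasound keeps half of the benefit of mpMRI when the data show less than that.

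**Working it through.** **Inputs.** Margin 0.76; historical ratio 0.52 (95% CI 0.45–0.60); mpMRI 0.93 and TRUS 0.48 (section 5.9.1). mpMRI 0.90, micro-ultrasound 0.85, 80% agreement, 120 subjects (sections 5.9.2 and 5.9.3). Prevalence 60% (section 5.9.1), so 72 cancers. mpMRI 88%, 70% and about 66%; systematic biopsy 48% (section 5.20).

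**The plan's own figure.** 0.48/0.93 = 0.516, given as 0.52. Margin = 1 − 0.5 × (1 − 0.52) = 0.76. This reproduces.

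**Retention on the plan's ratio scale.** Let R be the TRUS/mpMRI ratio. Retained share = (0.76 − R)/(1 − R).

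- R = 0.52: 0.24/0.48 = 50%
- R = 0.60 (upper limit): 0.16/0.40 = 40%
- R = 0.45 (lower limit): 0.31/0.55 = 56%

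**Retention by mpMRI sensitivity S, with TRUS held at 0.48.** Retained share = (0.76·S − 0.48)/(S − 0.48). The ratio that would keep half is (S + 0.48)/(2·S).

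| S | Source | 0.76·S | Share kept | Half-effect ratio |
|---|---|---|---|---|
| 0.93 | 5.9.1 | 0.707 | 50.4% | 0.758 |
| 0.90 | 5.9.3 | 0.684 | 48.6% | 0.767 |
| 0.88 | 5.20, same study | 0.669 | 47.2% | 0.773 |
| 0.70 | 5.20, targeted biopsy | 0.532 | 23.6% | 0.843 |
| 0.66 | 5.20, enrolment calculation | 0.502 | 12.0% | 0.864 |

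Setting the share to 0.5 gives 0.26·S = 0.24, so S must be at least 0.923. Of the mpMRI sensitivities the plan gives, only 0.93 meets this.

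**Half-effect ratio at the upper confidence limit.** 1 − 0.5 × (1 − 0.60) = 0.80.

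**Scale.** On the log-ratio scale the share is 1 − ln(0.76)/ln(R): 58% at R = 0.52, 46% at 0.60, 56% at S = 0.90, 55% at 0.88, 27% at 0.70 and 14% at 0.66.

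**Power if the margin were 0.80** (72 cancers, 0.85 against 0.90, 20% discordant, one-sided 5%). The standard error of the log ratio is √(0.20/(72 × 0.85 × 0.90)) = 0.0603. Then ln(0.9444/0.80)/0.0603 − 1.645 = 1.11, so power is 86.6%. A simulated score test for the paired ratio gives 79.5%. With 60 cancers the two figures are 81% and 72%. At 0.76 with 72 cancers they are 97.5% and about 93.5%.

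**The case against.** The strongest reply is that the margin is derived openly from a point estimate, and that its own inputs give exactly 50%. At 0.88 to 0.93 the shortfall is at most three percentage points, and on the log scale those values exceed 50%. This stands, and it limits the size of the point near the historical estimate. It does not rescue 'at least': the plan defines the effect on the plain ratio scale, and at the 0.60 limit both scales fall below 50% (40% and 46%).

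A second reply is that the 12–24% figures come from section 5.20, whose calculation (108 subjects, about 50% incidence, a 20% bound) is not the one in section 5.9, and that they hold TRUS at 0.48 while mpMRI falls. If the ratio stayed at 0.52, retention would be 50% at any mpMRI sensitivity. This also stands as a condition. Holding 0.48 is, however, section 5.20's own choice: it pairs 48% with 70% and cites it again beside 66%. In addition, section 5.8.1.3 counts systematic plus targeted cores, for which a targeted-only 0.66–0.70 may be too low. With 0.70 and 0.48 the combined sensitivity runs from 0.70 (nested) to 1 − 0.30 × 0.52 = 0.844 (independent), and retention from 24% to 44%, still below half.

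A reader might infer four stronger things that the documents do not support:

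- That the margin preserves only 12–47% on the plan's figures. Its defining inputs give 50%, and the power assumption gives 48.6%.
- That micro-ultrasound could pass with an observed ratio just above 0.76. Section 5.9.5 tests the lower bound. With mpMRI at 65/72 and about 14 discordant pairs, the observed ratio must be about 0.85: 55/65 = 0.846, with lower bound 0.846 × exp(−1.645 × √(14/(55 × 65))) = 0.763. What matters is what the bound excludes.
- That the margin must become 0.80. That value still keeps only 36% at mpMRI 0.70 and 27% at 0.66, so it does not secure half either.
- That the stated "80% power to reject the null hypothesis" shows a 0.80 margin was intended. About 80% is also obtained at 0.76 with one-sided 2.5% and 60 cancers.

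**Conclusion.** The retention claim is wrong as written. On the plan's scale, 0.76 retains 50% at the historical point estimate and 40% at its printed upper confidence limit; this needs no figure from outside the margin paragraph. With TRUS held at 0.48, it retains 48.6% at 0.90, 47.2% at 0.88, and about 24% and 12% at 0.70 and 0.66. The last two depend on section 5.20's inputs and on TRUS not falling with mpMRI.

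A pass may therefore fail to support a 50%-retention conclusion, depending on the mpMRI sensitivity seen in the trial. The finding concerns what a pass may be said to show. It does not invalidate 0.76 as a chosen threshold.

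**What to change.** 1. In section 5.9.1, delete or qualify 'at least 50%'. State that 0.76 retains 50% at the point estimate, 40% at the 0.60 limit, and less if mpMRI-targeted sensitivity is near 0.66–0.70.
2. Reconcile 0.93 (section 5.9.1) with 88% (section 5.20) for the same study, and say which applies to the endpoint definition used here.
3. State that passing 0.76 alone will not be reported as 50% retention. Report the observed lower bound also against 0.80 (half-effect at the confidence limit) and 0.84–0.86 (half-effect at mpMRI 0.70–0.66), labelled as supportive.

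The cost is a less favourable stated claim and a little more reporting, with no change to conduct or sample size.

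Changing the primary margin to 0.80 is an optional design choice. At 72 cancers, power would be about 79–87% depending on the test. It would be lower with the data exclusions allowed by sections 5.9.9 and 5.9.11 or with lower prevalence (72–81% at 60 cancers).

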### **5.9.2 Sample size**

The trial will include 120 subjects. It is not anticipated that additional subjects will be required, however if a subject drops out before the biopsy procedure they may be replaced as described in section 5.8.1.6.

### **5.9.3 Level of significance and power of the clinical investigation**

Assuming a micro ultrasound sensitivity of 0.85 and mpMRI performs at an expected 0.90 sensitivity, then 120 subjects would be required to provide 80% power to reject the null hypothesis, assuming 80% agreement between the methods.

PASS and MATLAB software were used for sample size calculations.

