## **5.7 Objectives and Hypothesis**

### ***5.7.1 Objectives***

**Primary Outcome:** Comparison of subject-level detection rate of clinically significant cancer (csPCa, defined as ISUP 2 or higher) between micro-ultrasound targeted biopsy and mpMRI targeted biopsy.

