### ***5.7.2 Hypothesis***

**Primary Hypothesis:** Micro-ultrasound provides non-inferior (10% margin) sensitivity to detect csPCa using targeted samples compared to mpMRI.

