#### **5.8.1.3 Endpoints**

##### **Primary endpoint**

The primary endpoint is the presence of clinically significant prostate cancer (csPCa) in each subject. The per-subject presence of cancer will be determined based on a positive biopsy from any sample, targeted or systematic. Patient-level sensitivity for a given imaging modality will be determined through systematic biopsy results plus targeted samples taken using only that modality. In this way we approximate clinical reality of using a given modality for systematic plus targeted biopsy.

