##### **Secondary endpoints**

Sensitivity of targeted-only samples for each modality will also be calculated in order to determine the effectiveness of a targeted only biopsy technique in each case. Presence of cancer per-target will also be assessed, along with detailed pathological findings, and targeting modality identifying the lesion. Size and shape of lesions will also be recorded from recorded images.

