### **5.9.5 Pass/fail criteria**

The primary outcome of the study will fail if micro-ultrasound targeted biopsy fails to identify cancer in significantly more subjects than mpMRI targeted biopsy. This will be quantified by testing against the lower one-sided 95% confidence interval bound of the ratio of the two sensitivities, which must not be less than 76%.

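### The power statement in 5.9.3 does not follow from the plan's own inputs: they give about 94% power against the 0.76 ratio, not 80%, and the sensitivity definition and margin it relies on are stated inconsistently

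*Combined protocol and SAP*

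**What the plan says.** Section 5.9.3 assumes sensitivities of 0.85 for micro-US and 0.90 for mpMRI, "then 120 subjects would be required to provide 80% power to reject the null hypothesis, assuming 80% agreement between the methods". It gives no significance level. The other inputs are elsewhere:

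- 5.9.1: "Power is based on the sensitivity of the test. Prevalence is assumed to be 60" per cent. The null hypothesis is a sensitivity ratio of 0.76 or less, and McNemar's test is to supply the confidence interval for the ratio, at a level written only as 1 − α.
- 5.9.5: the decision uses the "lower one-sided 95% confidence interval bound of the ratio of the two sensitivities, which must not be less than 76" per cent.

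The sensitivity being compared is described in two ways. The objective in 5.7.1 is a comparison "between micro-ultrasound targeted biopsy and mpMRI targeted biopsy", and 5.7.2 and 5.9.5 also speak of targeted samples or targeted biopsy. The primary endpoint in 5.8.1.3 instead says: "The per-subject presence of cancer will be determined based on a positive biopsy from any sample, targeted or systematic", and "Patient-level sensitivity for a given imaging modality will be determined through systematic biopsy results plus targeted samples taken using only that modality". Its secondary endpoints then add: "Sensitivity of targeted-only samples for each modality will also be calculated".

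Three margins appear. The primary hypothesis in 5.7.2 reads "Micro-ultrasound provides non-inferior (10% margin) sensitivity to detect csPCa using targeted samples compared to mpMRI". Sections 5.9.1 and 5.9.5 use a ratio of 0.76, which 5.9.1 also expresses as 24%. The literature review in 5.20 reports 108 subjects for non-inferiority within 20%, with about 50% incidence and sensitivities of about 66% (mpMRI) and 75% (micro-US).

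**The concern.** A sample-size statement should be reproducible from the inputs printed with it, and this one is not. The 80% agreement also matters for a second reason: whether it is attainable depends on which sensitivity is meant, and the plan defines the primary sensitivity in two incompatible ways. A reader cannot tell which quantity 0.85, 0.90 and 80% describe.

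The margin conflict carries the largest consequence. A lower bound between 0.76 and 0.90 would pass the rule in 5.9.5, yet fail the primary hypothesis in 5.7.2 if its 10% is read as a ratio of 0.90. Finally, McNemar's test addresses equality of two paired proportions. It does not itself produce a bound for a sensitivity ratio that could be compared with 0.76.

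**Working it through.** **Inputs.** N = 120 and prevalence 0.60, so n = 72 subjects with csPCa. Sensitivities p1 = 0.85 (micro-US) and p2 = 0.90 (mpMRI), ratio 0.944. Agreement 0.80, so discordance d = 0.20. Null ratio R = 0.76. One-sided α = 0.05 (5.9.5).

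**Cells among csPCa subjects.** The discordant cells sum to 0.20 and differ by 0.05: micro-US only 0.075, mpMRI only 0.125, both 0.775, neither 0.025.

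**Attempt to reproduce 80%.**

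*Log-ratio formula.* SE = √[d/(n·p1·p2)] = √[0.20/(72 × 0.765)] = 0.0603. Distance to the null = ln(0.944/0.76) = 0.2173. Power = Φ(0.2173/0.0603 − 1.645) = Φ(1.96) = 97.5%. For 80% power, (1.645 + 0.842)² × 0.20/(0.765 × 0.2173²) = 34.2 cancers, or 58 subjects (59 if cancers are rounded up first).

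*Score test of the paired ratio (Nam–Blackwelder/Tang).*

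- Null variance per subject from the constrained estimates: 0.76 × (0.0441 + 0.2675) = 0.2368.
- Variance under the alternative: 0.85 × 0.15 + 0.76² × 0.90 × 0.10 − 2 × 0.76 × (0.775 − 0.765) = 0.1643.
- Power = Φ{[√72 × (0.85 − 0.76 × 0.90) − 1.645 × √0.2368]/√0.1643} = Φ(1.50) = 93.3%.
- Exact multinomial enumeration gives 93.6%. Power of 80% needs 47 cancers, or 79 subjects.

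**Sensitivity to agreement and prevalence.** Sensitivities of 0.85 and 0.90 allow the neither cell to run from 0 to 0.10. Agreement among csPCa subjects is 0.75 + 2 × neither, so it lies between 75% and 95%. Exact score power against 0.76, one-sided 5%:

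| Cancers | 75% agreement | 80% | 95% |
|---|---|---|---|
| 72 (60% prevalence) | 89.9% | 93.6% | 99.8% |
| 65 (54%, from 5.20) | – | 91.2% | – |
| 60 (50%, from 5.20) | 84.9% | 89.0% | 99.2% |

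**Routes to about 80% at N = 120.** Each replaces at least one stated input:

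- Margin 0.80: 79.5%.
- One-sided 2.5% with 50% prevalence: 80.5%.
- One-sided 2.5% with 75% agreement: 81.9%.
- One-sided 2.5% alone is not enough: 87.6%.

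**Agreement under 5.8.1.3.** A subject has csPCa if any core is positive. Each modality is credited with the systematic cores plus its own targets. Every csPCa subject is therefore positive on at least one modality, and the neither cell is zero. Misses of 0.15 and 0.10 cannot overlap, so discordance is 0.25 and agreement is exactly 75%. Over all 120 subjects, if every subject without csPCa is a concordant negative, it is 0.40 + 0.60 × 0.75 = 85%. Neither figure is 80%. For targeted-only sensitivity, 80% is feasible, with 2.5% of cancers found by systematic cores alone.

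Suppose instead that 0.85 and 0.90 are targeted-only values but the combined quantity is primary. Assume that the shared systematic cores find 26–60% of the discordant cancers (5.20 gives 48% as the sensitivity of systematic biopsy). The combined ratio is then 0.961–0.979, and score power with 72 cancers is at least 98.9%.

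**The 10% margin.** With 72 cancers and 80% agreement:

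- Read as ratio 0.90: Φ[ln(0.944/0.90)/0.0603 − 1.645] = 19.9%; by exact calculation 18.1% (score) to 22.0% (log-Wald).
- Read as an absolute 0.10: Φ[0.05/√((0.20 − 0.0025)/72) − 1.645] = 24.5%; by exact calculation 22.2% (score) to 26.8% (Wald).

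**The case against.** The strongest points on the other side are these.

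- **An imaging-call reading.** The plan also tests specificity against a ratio of 0.67. That would be empty if a positive test meant a csPCa-positive biopsy. If the test is the imaging call, subjects without csPCa can also disagree. Overall agreement of 80% is then possible: from 0.80 = 0.60a + 0.40b, agreement of 75–95% in csPCa subjects pairs with 87.5–57.5% in the others. This stands as a further reading of the 80%, but the 89.9–99.8% range for 72 cancers already covers it.
- **Conditional impossibility.** The 80% agreement is impossible only if 0.85 and 0.90 are systematic-plus-targeted sensitivities. That is correct. It shows that 5.8.1.3 conflicts with 5.7.1, 5.7.2 and 5.9.5, and not that 80% is wrong on every reading.
- **Method.** The plan names no score test, and the answer runs from about 93% to 98% by method. That also stands, but no method tried gives 80% from the stated inputs.
- **Governing margin.** The power statement refers to the null hypothesis, which 5.9.1 prints as 0.76. The revision history says that the latest revision changed the statistical plan, so the 10% may be leftover text. That is plausible, but 5.7.2 is the current primary hypothesis and nothing marks it as superseded.
- **Consequence.** The power error is conservative, and McNemar's test may be shorthand for a paired-ratio interval. Taken alone, the arithmetic is a minor documentation fault. The margin and endpoint conflicts give the point its weight.

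**Conclusion.** The concern holds. From the stated inputs, power against 0.76 is about 94% by the score test and up to 97.5% by formula. Every feasible agreement leaves it at 89.9% or more with 72 cancers, and at 84.9% or more with 60. The stated 80% can be recovered only by changing an input. The agreement figure contradicts the primary-endpoint definition in 5.8.1.3 and fits only a quantity listed there as secondary, unless it refers to imaging calls across all subjects.

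Against 0.76 the trial is not underpowered and 120 subjects are enough. If the 10% of 5.7.2 governs, power is about 18–27%, so the margin must be settled before any power is quoted. These figures assume the sensitivities in 5.9.3, a one-sided 5% level and no exclusions. Subjects dropped for incomplete or incorrect data (5.9.9 to 5.9.11) would lower them.

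**What to change.** 1. State one margin and its scale in 5.7.2, 5.9 and 5.20. Align the 108-subject calculation in 5.20 or label it superseded.
2. State whether targeted-only or systematic-plus-targeted sensitivity is primary, use it throughout 5.7.1, 5.7.2, 5.8.1.3 and 5.9.5, and restate 5.9.3 for it, including the significance level.
   - If targeted-only with 0.76: *With 120 subjects and 60% prevalence, 72 subjects with csPCa are expected. If targeted-only sensitivities are 0.85 (micro-US) and 0.90 (mpMRI), with 80% agreement among subjects with csPCa, a one-sided 5% score test of the paired ratio against 0.76 has about 94% power (91% with 65 cancers, 89% with 60).*
   - If systematic-plus-targeted with 0.76: delete the 80% agreement, because the two sensitivities fix it (75% for 0.85 and 0.90, about 90% power). Confirm that 0.85 and 0.90 are meant for the combined samples.
3. In 5.9.1, replace McNemar's test as the interval method with a score confidence interval for the ratio of paired proportions (Nam–Blackwelder/Tang). Its lower one-sided 95% bound is what 5.9.5 compares with 0.76.

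The cost is wording and one rerun of the sample-size program. If 0.76 is the governing margin, no extra patients or procedures are needed.
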